We also have studied whether the immunologic changes in serum anti-PLA2R levels parallel the clinical reduction in proteinuria in response to RTX in patients with MN. Serial serum samples from our 2 cohorts of MN patients treated with RTX (cohort 1 treated with 1 g of RTX at d.1 and d.15) and cohort 2 (treated with 4 weekly doses of 375 mg RTX), were assayed for anti-PLA2R antibodies.⁷⁷ Ten out of 15 (67%) patients in cohort 1 and 16/20 (80%) in cohort 2 had anti-PLA2R reactivity in their baseline serum samples. When the 2 cohorts were combined, the baseline distribution of cases with anti-PLA2R positivity was not significantly different when compared to the final clinical groupings of complete remission (CR), partial (PR) limited or no remission (NR), (p=0.61). However, an anti-PLA2R level below 500 arbitrary units at 9-12 months after initiation of treatment was significantly different among these groups: in the complete remission (CR) group 100% had a reduction to this level, in the PR group 88% had reduction to this level but in the limited response (LR) group only 50% had a reduction and in those with no response only 17% had a reduction to this level. (p=0.006). Median proteinuria at 9, 12, and 15-18 months was consistently lower in those subjects with undetectable or very low anti-PLA2R levels versus those with higher levels. In the group in which anti-PLA2R disappeared, 86% were in complete or partial remission at the final time point: 4 complete remissions (CR), 14 partial remissions (PR), 1 limited remission (LR), and one non-responder (NR). Perhaps most relevant was, in those patients with decreases in anti-PLA2R, the decline almost always preceded the reduction in proteinuria by months. In addition, 1 patient who had attained remission and who had become anti-PLA2R negative following RTX became antibody positive at the time of his relapse. Thus, in at least these two cohorts of MN patients with anti-PLA2R antibodies at the start of treatment, post-RTX anti-PLA2R levels correlated with and seemed to precede clinical response to RTX (Figure 3). These results suggest that monitoring anti-PLA2R autoantibody levels may provide a window onto the immunologic effects of treatment on the course of IMN, and allow a more specific and an earlier means of determining treatment effectiveness compared to the clinical response of decreasing proteinuria. This observation is understandable given the nature of the deposits and proposed pathophysiology of IMN. Even if the B cells producing anti-PLA2R were completely eliminated and all circulating anti-PLA2R removed, the immune deposits would persist in the subepithelial space until cleared. Supportive evidence of this was seen in repeat kidney biopsies performed in RTX-treated IMN patients after they had entered complete clinical remission.⁷⁸ There are other important implications to the antibody story to consider if they truly parallel immunologic disease activity. Secondary chronic changes in IMN such as focal sclerosis or interstitial damage from prolonged disease activity may lead to indefinite persistence of low-level proteinuria, despite full clearance of immune deposits. This is the case seen in kidneys made proteinuric in the Heymann nephritis model and subsequently transplanted into naïve hosts.⁷⁹ This may explain our observation that not only does the decline in proteinuria lag behind that of anti-PLA2R, but also that the median proteinuria never reaches zero even by 24 months. It may also explain why most clinical responses are partial remissions (rather than complete) in the group that cleared anti-PLA2R. It will be important to see whether these patients will continue to have a further slow decline in proteinuria with further follow-up, similar to patients with IMN who undergo spontaneous remission.⁸ It may also help to explain why even patients with only partial remissions are still associated with good long term outcomes, i.e. in

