Serum samples from all 126 subjects will be collected at the Screening visit (when applicable), Time 0, and months 3, 6, 9, 12, 18, and 24. Serum samples will be collected at the individual sites by the study coordinator and stored in a dedicated -20° freezer until a point when they can be shipped in bulk to [name] at Mayo Clinic, Rochester, Minnesota. Mayo Clinic will then send the samples in bulk to [name] at the Manchester Royal Infirmary in the UK. The sera will be tested in batches for reactivity toward immobilized recombinant PLA2R by ELISA, with appropriate positive and negative controls. Upon completion of the study, we will correlate response to treatment in each group to the baseline presence and/or titer of anti-PLA2R. A major hypothesis to be addressed is whether there is a difference in treatment response between those subjects who are initially anti-PLA2R negative versus those who possess circulating anti-PLA2R. In those subjects who are initially positive for anti-PLA2R, we will also correlate the primary endpoint (remission status) to anti-PLA2R titers throughout and at the end of the study.

For those in the remission cohort (see ancillary studies), additional serum samples will be collected from those that achieve partial or complete remission or $\geq 50\%$ reduction in proteinuria by 12 months at additional time points as follows:

- For patients in the CSA arm that are in partial or complete remission or $\geq 50\%$ reduction in proteinuria at 12 months additional samples will be collected at months 13, 14, 15, 16, 17, 20, 22, 26, 28, 30, 32, 34, and 36; for those who achieve complete remission at 6 months additional samples will be collected at months 7, 8, 10, and 11 then at 14, 16, 20, 22, 26, 28, 30, 32, 34, and 36.
- For patients in the RTX arm that achieve partial or complete remission or $\geq 50\%$ reduction in proteinuria at 12 months additional samples will be collected at months 14, 16, 20, 22, 26, 28, 30, 32, 34, and 36; for those in the RTX arm that have achieved complete remission at 6 months, additional samples will be collected at months 10, 14, 16, 20, 22, 26, 28, 30, 32, 34, and 36.

Whole blood for these particular serum samples may be collected at a peripheral lab and shipped to the individual study site within 48 hours for processing and storage in a -20° freezer as described in the ancillary studies section later in this protocol.

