Investigators in the study will be blind to the results of anti-PLA2R antibodies until the study is completed. The rationale is to avoid bias in the treatment of these patients. Although ideally patients would be stratified to the different arms based on the results of their initial anti-PLA2R test in order to avoid potential imbalance this will not be possible for practical and financial reasons. Given the relatively small number expected to be negative, it is unlikely this will bias the balance between positive and negative patients at randomization.

Histopathology

Prior to randomization, a report documenting the results of the histology review including, light microscopy, immunofluorescence and electron microscopy results, as well as percentage of global and segmental glomerular sclerosis, tubulo-interstitial index, and immunofluorescence findings will be submitted to the DMCC and reviewed by the study P.I.

Following randomization, biopsy slides will be centrally reviewed on an on-going basis (but as soon as possible following randomization) by the Pathology Department at Mayo Clinic Rochester and/or the Pathology Department at the University Hospital Network, Toronto.

Quality of life measures

Psychosocial response to illness and its treatment may play an important role in overall adjustment and illness management. Research from a variety of chronic illness populations, including steroid resistant FSGS and chronic kidney disease (CKD), has consistently linked physical and psychosocial variables with health outcomes. These findings highlight the significant burden experienced by adults with uncontrolled nephrotic syndrome. Little is known about the impact of MN or its treatment on patient reported outcomes. Due to the severity of this disease and the potential risk for progression in these patients, psychosocial factors may play an important role in understanding their response to treatment. In addition to evaluating the safety and efficacy of RTX and CSA, it is essential to assess the individual's perception of his/her quality of life relative to disease status and therapeutic response. Quality of life will be assessed by patient self-report using the modified KDQOL questionnaire form at Time 0, 6, 12 and 24 months.

Table 2a: Test Schedule and Monitoring for Cyclosporine Treatment Arm

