Sample size estimation: The primary study goal is to compare the long-term efficacy of RTX (given at baseline and repeated at 6 months) with CSA (12 months treatment + 2 months taper) using proteinuria response 24 months after randomization. Proteinuria positive response will be defined as attaining and maintaining CR or PR at 24 months after randomization. We propose to establish that the RTX treatment is non-inferior to the CSA. RTX will be considered non-inferior to CSA if the response rate of the RTX arm is at most 15% worse than that of CSA arm. In addition we will compare the quality of life (QOL) and adverse event (AE) profile over the course of the treatment period. The preliminary data has indicated that CSA is effective in inducing a CR/PR of proteinuria in between 60 and 75% of MN cases.^{48, 51} However, nephrotic syndrome (NS) relapses may be as high as 50% once CSA is discontinued.⁸⁵ Thus, we estimate a CR/PR rate in patients treated with CSA of 30-50% at 24 months after randomization.⁸⁵ Similar remission and relapse rates with the use of Tacrolimus (another calcineurin inhibitor) have been reported by Praga et al.⁵⁶ In this latter study, almost half of the MN patients had a relapse of the nephrotic syndrome after tacrolimus was discontinued.⁵⁶ On the other hand, based on the long term follow up on the 35 patients treated with RTX from our 2 studies, we estimate the relapse rate to be <10% at 24 months.^{71, 75} We observed a CR/PR rate at 12 months, very similar to the rate for calcineurin inhibitors i.e. 60%, and in our second study completed recently, we observed an 80% CR/PR rate at 24 months, implying that RTX had a ~20% failure rate with 95% (CI 6% to 44%). To be conservative for the sample size estimation, we considered a maintained CR/PR rate at the low end of our previous experience, 55% CR/PR for RTX at 24 months and at the high end of our experience with CSA (CNI therapy) CR/PR for CSA of 45%. We propose a non-inferiority trial with non-inferiority margin $\delta = 15\%$, with the null hypothesis of $\pi_{RTX} - \pi_{cyclosporine} < \delta$, where π_{RTX} and $\pi_{cyclosporine}$ are the proportions of patients with CR/PR at 24 months in treatment arms of RTX and CSA, respectively. Under these assumptions, and a one sided alpha of 0.025, enrollment of 63 evaluable patients per study arm is required to achieve 80% power to show that the RTX is not inferior. For the intent to treat (ITT) analysis we will consider all patients lost to follow up to be non-responders so no correction to the sample size is needed for dropouts. With 63 patients per arm we will have 80% power to detect moderate differences of .6 standard deviations for continuous measures or around .25 for proportions for the comparisons of the QOL and AEs.

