
Statistical and Analytical Plan: All demographics and entry laboratory data will be summarized by treatment group. Frequency distributions will be used to describe categorical values and basic summary statistics (mean, standard deviation, median, and inter-quartile range) will be used to describe continuous values. To provide more reliable estimates and minimize the “regression to the mean effect” duplicate urine measurements obtained at baseline (Time 0), 6, 12, 18 and 24 months will be averaged. The chi-square test and logistic regression will also be used to compare the percent of patients with remission at 6, 12, 18, and 24 months adjusting for treatment center and the baseline

proteinuria (UP<8g/24h vs >=8g/24h). Odds ratios and associated 95% confidence intervals will be estimated. The formal test for the primary endpoint will be based on the significance of the treatment group factor in the logistic regression model for UP failure at month 24. The Wilcoxon rank-sum test and ordinal logistic regression will be used to compare the ordered remission status outcome (1=CR, 2=PR, 3=NR) between treatment groups. Longitudinal methods for categorical outcomes (e.g. generalized estimating equation or GEE models) will be used to compare remission status profiles between treatment arms. Unless otherwise noted, all tests will be two-sided with alpha level 0.05.

For repeated measures such as urine protein, individual rates of change will be estimated using within-patient linear regression analyses (including data from all visits). Because of the non-linearity of the changes in proteinuria log transformation estimates will be used. Renal function readings will be censored at initiation of dialysis or renal transplant. Additionally, mixed effects models, assuming a random center effect, and a random slope of creatinine clearance and/or reciprocal of creatinine and intercept for each patient will be fit using data from all visits. These models allow comparison of the average slope between groups, while taking into account that each patient's slope may be based on a variable number of readings. Treatment group comparisons regarding quality-of-life scales will be done using repeated measures analyses and mixed effects models.

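### Baseline anti-PLA2R status, which the protocol would ideally have stratified on, is missing from the remission models, and the hypothesis about it has only within-group correlations and no pooled model

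*Combined protocol and SAP*

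**What the plan says.** **Randomization.** The list is stratified by site only (Randomized Treatment Groups). The Anti-PLA2R Assay section says stratifying on the initial antibody result would be ideal for avoiding imbalance, but is not possible for practical and financial reasons. It adds: "Given the relatively small number expected to be negative, it is unlikely this will bias the balance between positive and negative patients at randomization".

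**How many are negative.** The section on anti-PLA2R levels and response to treatment reports that "Ten out of 15 (67%) patients in cohort 1 and 16/20 (80%) in cohort 2 had anti-PLA2R reactivity" at baseline. The DNA Testing paragraph puts positivity in the pilots at roughly 70%.

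**What is measured.** Serum for the assay is taken at Time 0 from all 126 subjects. Investigators stay blind to the results until the study is completed.

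**Remission models.** The Statistical and Analytical Plan compares remission at 6, 12, 18 and 24 months "adjusting for treatment center and the baseline" proteinuria (below 8 versus 8 g/24h or more). There is no antibody term, and no reason is given for leaving it out.

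**Analysis by status.** After study completion, "we will correlate response to treatment in each group to the baseline presence and/or titer of anti-PLA2R". The next sentence names as a major hypothesis that treatment response differs between initially negative and initially positive subjects. The statistical sections give no model, interaction term, alpha or power for this.

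**The concern.** There are two separate gaps.

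First, the protocol singles out one baseline factor as worth balancing, explains why the randomization cannot balance it, and then does not adjust for it. The obstacles to stratifying do not apply at the analysis: the sample is already taken from everyone, and the result is not needed before randomization. The reassurance about small numbers is also weak, because about a quarter of the pilot patients were negative.

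Second, the hypothesis about status has no analysis matched to it. It could be prognostic (do negatives and positives remit at different rates?) or an interaction (does the rituximab versus cyclosporine difference depend on status?). Correlating within each arm halves the data for the first question and does not address the second. The protocol hopes antibody levels will influence future treatment protocols, so an unclear answer has a cost.

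**Working it through.** **The plan's own figure.** Inputs from Sample size estimation: remission 55% (RTX) and 45% (CSA), RTX acceptable if "at most 15% worse than that of CSA arm", and "one sided alpha of 0.025, enrollment of 63 evaluable patients per study arm is required to achieve 80% power". With unpooled variance:

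n = (1.960 + 0.842)² × (0.55×0.45 + 0.45×0.55) / (0.10 + 0.15)² = 7.85 × 0.495 / 0.0625 = 62.2, so 63 per arm.

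The figure reproduces (power 80.5% at 63 per arm), and nothing below changes it.

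**Expected negatives.** Pilots: 5/15 + 4/20 = 9/35 = 26% (exact 95% CI 12% to 43%). Applied to 126 this is about 32, with 25 at 20% and 42 at 33%, the two cohort rates.

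**Chance imbalance.** Split 32 negatives at random over 63 + 63 (hypergeometric, ignoring site blocking).

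- SD of the number in one arm = √(63 × 32/126 × 94/126 × 63/125) = 2.45.
- SD of the difference in percent negative = 2 × 2.45/63 = 7.8 points.
- P(difference of 10 points or more) = 0.15, and 0.15 to 0.19 across the counts computed between 25 and 42. P(15 points or more) = 0.07.

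A normal approximation gives 0.20 for 10 points. The exact value is lower because, with 32 negatives, the difference moves in steps of 2/63 = 3.2 points, and the smallest step past 10 is 8/63 = 12.7.

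**Effect on the treatment difference.** The documents give no remission gap by status, so it is assumed. Shift = gap × imbalance. For a 10-point imbalance:

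| Assumed gap | Shift |
|---|---|
| 10 points | 1 point |
| 20 points | 2 points |
| 30 points | 3 points |

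The margin is 15 points, and the standard error of the unadjusted difference is √(0.495/63) = 8.9 points.

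**Precision of the analyses by status.** Assumptions: response variance 0.25, 32 negatives split evenly (16 and 47 per arm), two-sided 0.05, 80% power (multiplier 2.80).

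| Analysis | Standard error | Detectable |
|---|---|---|
| Status effect within one arm | √[0.25(1/16 + 1/47)] = 0.145 | about 41 points |
| Status effect pooled over arms | √[0.25(1/32 + 1/94)] = 0.102 | about 29 points |
| Arm-by-status interaction | √[2 × 0.25(1/16 + 1/47)] = 0.205 | about 57 points |

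Power for a 30-point interaction is about 31%.

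**Why within-group results cannot stand in for an interaction.** Suppose status shifts remission by the same 30 points in both arms (assumption), so that there is no interaction. Each within-arm test then has power of about 0.545. The chance that exactly one is significant is 2 × 0.545 × 0.455 = 0.50. Discordant within-arm results would be common with no difference in treatment effect.

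**The case against.** The case for leaving the plan alone has real substance.

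- **Status may not be prognostic.** The pilots found no significant association between baseline positivity and final remission group (p=0.61). With 35 patients, all on rituximab, that excludes little. It is nevertheless the only evidence in the documents on the point, and the gap used above has no support there.
- **Randomization already covers chance imbalance.** It is part of the sampling error of the unadjusted difference and does not inflate type I error. With 26% negative, a 20- to 30-point gap explains 0.26 × 0.74 × gap² / 0.2475, about 3% to 7% of the outcome variance. Adjustment would reduce the standard error only from 8.9 to about 8.7 or 8.6 points.
- **Negatives may be fewer than in the pilots.** The protocol says sensitivity is higher in new-onset nephrotic patients. Previously treated patients who relapsed are also eligible, however, so the direction is uncertain. Fewer negatives would reduce imbalance but also make the analyses by status less precise.
- **The antibody work is exploratory in tone,** antibody levels are a secondary endpoint, and the proposed interaction is underpowered.
- **The primary model is already loaded:** up to 25 centers with about 63 remissions expected (63 × 0.55 + 63 × 0.45).

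These points stand, and they limit the priority for the primary comparison. They do not supply an analysis for the stated hypothesis.

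A reader might infer three stronger things that the documents do not support. One is that the covariate was omitted because negatives are few; that sentence concerns stratifying the randomization only. Another is that the pilot data show the primary comparison would be biased; they undercut only the claim of small numbers. The third is that the plan will compare a p-value in one arm with a p-value in the other; no section says so, and the test of the hypothesis is simply unspecified.

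**Conclusion.** The point holds as a cheap improvement with two parts of unequal weight.

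For the primary comparison it has lower priority. About 32 negatives (25 to 42) give roughly a 15% chance of a 10-point or larger imbalance. The resulting shift is 2 to 3 points of the 15-point margin, in either direction, and only if remission differs by 20 to 30 points by status. That gap is assumed. This is a modest loss of efficiency, and the validity of the primary test is not in question.

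For the antibody hypothesis the case is firmer, because it does not depend on status being prognostic. Under the prognostic reading, within-group correlation detects about 41 points where a pooled analysis detects about 29. Under the interaction reading, it does not answer the question at all. These figures rest on the pilot share of negatives, an even split between arms and a response variance of 0.25.

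**What to change.** Make both changes before antibody results are unblinded.

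1. Prespecify Time 0 anti-PLA2R status (positive or negative, with the cut-off stated) as a covariate in the month-24 remission model, at least as a supportive analysis, and in the month 6, 12 and 18 models.
2. State whether the hypothesis in the Anti-PLA2R Assay section is prognostic or a treatment interaction. Replace the within-group correlations with one model containing arm, status and arm-by-status. Report the pooled status effect and the interaction, each with a 95% confidence interval, label them exploratory, and say that power reaches 80% only for an interaction of about 57 points.

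The cost is SAP wording and one or two extra parameters in a model that already adjusts for up to 25 centers. The conditional odds ratio for treatment will change slightly, which is a reason to keep the adjusted month-24 model supportive if the sponsor prefers. No new samples or patients are needed.
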